1.1. Synopsis

Protocol Title:

Multicenter, Randomized, Double-blind Placebo-controlled, Crossover Study to Investigate Effects of V117957 in Female Subjects with Interstitial Cystitis/Bladder Pain Syndrome

Brief Title:

Study of V117957 in Interstitial Cystitis/Bladder Pain Syndrome

Rationale:

V117957 is a selective partial agonist of the nociceptin/orphanin-FQ peptide receptor. V117957 inhibits bladder afferents following systemic administration in rats leading to reduction in the frequency of rhythmic bladder contractions without affecting the magnitude of contraction. V117957 had mixed effects in standard models of overactive bladder in rats (spinal cord injury and bladder outlet obstruction) and was anti-nociceptive in a rat model of interstitial cystitis / bladder pain syndrome (intraperitoneal administration of cyclophosphamide). Based on these animal observations, it is hypothesized that V117957 may be effective in treating symptoms of interstitial cystitis and bladder pain syndrome in humans.

Objectives and Endpoints:

Objectives	Endpoints
Primary	
Evaluate effects of V117957 on bladder pain/discomfort in subjects diagnosed with interstitial cystitis/bladder pain syndrome (IC/BPS) compared to placebo	
 • Bladder pain/discomfort score. 
 – Each evening and morning subject will respond to question “Please indicate the worst bladder pain/discomfort you have had overnight/over the day” using an 11-point numeric rating scale.
[REDACTED]	[REDACTED]

Safety	
Assess safety and tolerability of V117957	Adverse events, Clinical laboratory values, Electrocardiograms, Physical examination, Vital signs, Columbia-Suicide Severity Rating Scale (C-SSRS), Epworth Sleepiness Scale (ESS)

Overall Design:

Phase 1b, multicenter, randomized, double-blind, placebo-controlled, crossover study.

Brief Summary:

The purpose of this study is to investigate the effects of oral administration of 1 mg/day V117957 each evening in female subjects with interstitial cystitis/bladder pain syndrome as compared to placebo. The study will consist of a Screening/ Washout Period (up to 2 weeks), Single-blind Placebo Run-in Period (2 weeks), Double-blind Treatment Period (8 weeks), Single-blind Placebo Washout Period (1 week), and Follow-up Period (up to 1 week).

Number of Participants:

It is estimated that up to 150 subjects will be screened to yield approximately 75 subjects who will enter Single-blind Run-in Period to yield approximately 44 subjects who will enter the Double-blind Treatment Period. A sample size of 38 (completers) will have 81% power to detect a treatment difference of bladder pain/discomfort mean scores of 0.5, assuming a standard deviation of differences of 1.4, using a paired t-test with a 10% one-sided significance level. Assuming a 15% dropout rate, a sample size of 44 would be needed.

Treatment Groups and Duration:

V117957 (6-weeks) and Placebo (5-weeks).

Schema:

Phase Period	Pre-randomization			Post-randomization									
	Screening/ washout	Single-blind Run-in		Double-blind Treatment								Single- blind washout	Follow- up
Day	-28 to -16	-15	-1 ^A	1	14	15	28	35	42	49	56	63	70
Clinic Visit	V1		V2		V3		V4		V5		V6	V7	V8
Phone call ^B				P1		P2		P3		P4			
Treatment		Placebo		V117957 or Placebo								Placebo	

^A At visit 1 subject must meet all inclusion/exclusion criteria. At visit 2, if subject has met all randomization eligibility criteria they may be dispensed double-blind study-drug. ^B Phone contact between clinic visits to assess tolerability and review diary/dosing instructions.

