1.4.1. Primary Efficacy Analyses

The baseline, post-baseline and change from baseline for bladder pain/discomfort scores over last 12 hours (morning and night) will be summarized by treatment group using descriptive statistics and presented graphically. Changes from baseline to endpoint in mean bladder pain/discomfort scores will be analyzed by mixed model with treatment, period and sequence as fixed effects, subject within the sequence as a random effect and baseline as a covariate. Comparison of the active treatment to placebo will be tested at the one-sided significance level 0.10 by means of the corresponding contrast. Plots of the least square mean change from baseline and 90% confidence intervals will be produced by treatment group.

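### Is a sample size of 44 too small to leave 38 completers at 15% dropout?

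*Combined protocol and SAP*

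**What the plan says.** Everything relevant to the calculation is in the Synopsis (section 1.1) under Number of Participants. The power statement is for completers: "A sample size of 38 (completers) will have 81% power to detect a treatment difference". The difference to be detected is 0.5 on the mean bladder pain/discomfort score, "assuming a standard deviation of differences of 1.4", "using a paired t-test with a 10% one-sided significance level". The same error rate appears in section 1.4.1, where the contrast of active treatment with placebo is "tested at the one-sided significance level 0.10".

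The allowance for dropout is one sentence: "Assuming a 15% dropout rate, a sample size of 44 would be needed". The recruitment forecast just before it is looser and speaks of "approximately 44 subjects who will enter the Double-blind Treatment Period". The documents do not say how the 15% was applied or how the result was rounded.

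**The concern.** A dropout rate is normally a fraction of those who start. To end with 38 after losing 15%, one divides 38 by 0.85 and rounds up, since a number described as needed should not fall below its target. That gives 45, not 44. In the other direction, 44 subjects at 15% dropout leave 37.4 on average, below 38. Ending with exactly 38 of 44 means losing 6, which is 13.6%.

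So 38, 15% and 44 do not fit together under the strict convention. These few lines are the only numerical justification for the size of the trial in the documents. If the slip meant that the trial fell short of its stated power, or if it pointed to a wrong method elsewhere in the calculation, it would need correcting.

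**Working it through.** **Inputs**, all from section 1.1: 38 completers, difference 0.5, SD of within-subject differences 1.4, paired t-test at one-sided 10%, dropout 15%, stated total 44, stated power 81%. Section 1.4.1 confirms the one-sided 0.10.

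**Step 1: reproduce the stated power.** Power of the paired t-test is the probability that a noncentral t variable with n − 1 degrees of freedom and noncentrality (0.5/1.4) × √n exceeds the 90th percentile of the central t. At n = 38 the noncentrality is 0.3571 × 6.164 = 2.20, and power is 81.47%, or 81% to the nearest whole percent. The normal approximation gives 82.1%. The plan's figure therefore reproduces, by the exact method.

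**Step 2: the dropout allowance.**

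| Rule | Calculation | Result |
|---|---|---|
| Divide by the completion rate, round up | 38/0.85 = 44.71 | 45 |
| Divide by the completion rate, round down | 38/0.85 = 44.71 | 44 |
| Add 15% to the completers, round up | 38 × 1.15 = 43.70 | 44 |

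The first rule is the stricter and better one. Either of the others produces the printed 44, and the text does not show which was used.

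**Step 3: expected completers.** From 44: 44 × 0.85 = 37.4. From 45: 45 × 0.85 = 38.25. The shortfall against 38 is 0.6 of a subject.

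**Step 4: what that does to power** (same formula as step 1).

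| Completers | Power |
|---|---|
| 36 | 79.8% |
| 37 | 80.7% |
| 38 | 81.5% |

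The number of completers will vary, so I also averaged power over a binomial distribution in which each subject independently completes with probability 0.85. That independence is an assumption. The average is 80.9% with 44 randomized and 81.6% with 45, so the extra subject is worth 81.6 − 80.9 = 0.7 percentage points. At 44 the average still prints as 81%.

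**The case for a change.** The strongest case for a correction is that the sentence is unqualified. The word that makes 44 approximate belongs to the recruitment forecast, not to the sentence about what is needed. Neither route to 44 is good practice: adding 15% to the completers applies the rate to the wrong base, and rounding down leaves the expected count under the target. Under the binomial assumption the chance of reaching at least 38 completers is 50.3% from 44 and 63.9% from 45, which sounds material. And restating the line would cost nothing.

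The arithmetic in this stands, and so does the remark about where the qualifier sits. The contrast of 50.3% with 63.9% carries little weight, because it treats 38 as a pass mark. The plan's aim is 81% power, and 37 completers meet that to the nearest percent; the chance of at least 37 from 44 is 66.3% on the same assumption. Power changes by less than a percentage point from one completer to the next, so nothing turns on 38.

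Two further points weaken the case. First, completers are only a proxy for the information analysed. Efficacy is analysed in the full analysis population (sections 1.3 and 1.4), which requires randomization, study drug and one valid efficacy measurement, and the primary model in section 1.4.1 has a random subject effect. A subject who stops early but has data on both treatments still contributes a within-subject comparison. Second, 45 is not plainly the better number for a crossover: if there are two sequences of equal size (an assumption, since the number is not given), 44 divides evenly and 45 does not.

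**Conclusion.** No change is called for, because none would gain anything. Under strict rounding 44 is one subject short of 45, or 2.3% (1/44), and that is the whole of the discrepancy. The trial as sized still has its stated power: 80.7% at 37 completers, 80.9% on average from 44, against 81.6% from 45. The test, the analysis population and the reading of the results would be the same under either number, and recruitment is in any case planned only to about 44.

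This rests on the plan's own inputs (difference 0.5, SD of differences 1.4, one-sided 10%, 15% dropout) and, for the averaged figures, on independent dropout. If the synopsis is reopened for another reason, the line could say that 44 subjects at 15% dropout leave about 37 completers with about 81% power. That would be a courtesy to the reader and would not alter the plan.

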1.2. Schedule of Assessments

Table 1. Schedule of Assessments: Pre-randomization Phase

Period	Screening/washout	Single-blind Run-in	
Day ^A	-28 to -16 ^H	-15	-1
Clinic Visit	V1 ^B	V1	V2
Assessment			
Informed consent	X		
Medical history	X		
Demographics	X		
Inclusion/exclusion	X		
Physical exam, full	X		
Physical exam, brief		X ^F	X
Vital signs	X	X ^F	X
Clinical labs (chem/heme/urine)	X	X ^F	X
Urine culture test	X	X ^F	X
Urine drug screen	X		X
Serum pregnancy test	X		
Urine pregnancy test		X ^F	X
12-lead ECG	X	X ^F	X
Concomitant medications	X	X ^F	X
Adverse events	X	X ^F	X
ESS		X ^F	X
C-SSRS	X	X ^F	X
Cystoscopy ^C	X		
Hunner's Lesion Assessment ^D	X		
BPIC-SS	X	X ^F	X
ICSI	X	X ^F	X
ICPI	X	X ^F	X
SGRA			X
SISQ (diary)		Once daily, in morning	
Pain Diary assessment ^E		Twice daily, in morning and evening	
Void Diary assessment (includes PPIUS)		During the week prior to clinic visit (V2), subject will record micturition time, type, and urgency for each episode for a minimum of 3 and up to 7-days; and will also record urine volume during 2-day weekend (or other timeframe convenient to subject work/life schedule). Note: The urine volume collection is mandatory during the Run-in Period and optional (but encouraged) during Double-blind Treatment period.	
Study drug dosing (diary)		Once daily, in evening	
Diary/dosing instruction		X ^F	X
Dispensing study drug		X ^F	X
Drug accountability			X
IC/BPS Symptoms characterized		X ^{FG}	
Randomization criteria checklist			X
Randomization			X

BPIC-SS=Bladder Pain/ Interstitial Cystitis Symptom Score; CSSRS=Columbia-Suicide Severity Rating Scale; ECG=Electrocardiogram; ESS=Epworth Sleepiness Scale; ICSI=O'Leary-Sant Interstitial Cystitis Symptom Index; ICPI=O'Leary-Sant Interstitial Cystitis Problem Index; NSQS=Nocturia Sleep Quality Scale; PPIUS= Patient Perception of Intensity of Urgency Scale; SGRA=Subject Global Response Assessment; SISQ= Symptom Impact on Sleep Questionnaire.

^A visit window is ±3 day. ^B Visit 1, Day -15, is end of Screening/Washout Period and start of the Single-blind Run-in Period. At this visit, a subject that has met all inclusion/exclusion criteria, has stopped current prohibited medications, and completed all study procedures, will be dispensed single-blind study-drug with instruction to ingest first dose that evening 30 minutes before bedtime. ^C ^D Cystoscopy not required for enrollment; however, if available cystoscopy results within last 5 years should be recorded on eCRF. ^E pain assessment to be completed every 12 hours. ^F Item must be completed at the clinic visit on the same day that study drug is dispensed to subject; the

subject will ingest first dose of study drug that evening. ^G [REDACTED] this must be completed at the clinic visit on the same day that study drug is dispensed to subject; the subject will ingest first dose of study drug that evening. ^H

Table 2 Schedule of Assessments: Post-randomization Phase

Period	Double-blind Treatment									Single-blind washout	Follow-up	
	Day -1	1	14	15	28	35	42	49	56			
Day	-1	1	14	15	28	35	42	49	56	63	70	
Clinic visit ^A	V2 ^B		V3		V4		V5		V6	V7/ EOT/ET	V8/ EOS ^C	
Phone call ^D		P1		P2		P3		P4				
Assessment												
Physical exam, brief	See Table 1, V2 Day -1		X		X		X		X	X		
Vital signs			X		X		X		X	X		
Clinical labs (chem/hem/urine)			X		X		X		X	X		
Urine culture test			X		X		X		X	X		
Urine drug screen										X		
Serum pregnancy test										X		
Urine pregnancy test			X		X		X		X			
12-lead ECG			X		X		X		X	X		
Concomitant medications			X	X	X	X	X	X	X	X	X	X
Adverse events			X	X	X	X	X	X	X	X	X	X
ESS			X		X		X		X	X		
C-SSRS			X		X		X		X	X		
[REDACTED]												
Pain Diary assessment			Twice daily, in morning and evening ^E									
Void Diary assessment (includes PPIUS)		During the week prior to each clinic visit (V3, V4, V5, V6, and V7), subject will record micturition time, type, and urgency for each episode for a minimum of 3 and up to 7-days, and will also record urine volume during 2-day weekend (or other timeframe convenient to subject work/life schedule). Note: The urine volume collection is mandatory during the Run-in Period and optional (but encouraged) during Double-blind Treatment period.										
Study drug dosing (diary)		Once daily, in evening.										
Diary/dosing instruction	See Table 1, V2 day -1	X	X	X	X	X	X	X	X			
Dispensing Study Drug		X	X		X		X		X			
Drug accountability			X		X		X		X	X		

[REDACTED] PPIUS= Patient Perception of Intensity of Urgency Scale; [REDACTED]. V=visit, P=phone.

^A Visit window is ±3 day.

^B Visit 2, Day -1, is end of Single-blind Run-in Period and start of the Double-blind Treatment Period. At visit 2, a subject that has met all inclusion/exclusion criteria, has met all randomization eligibility criteria, and has completed all study procedures, will be dispensed double-blind study-drug with instruction to ingest first dose that evening 30 minutes before bedtime. ^C May be phone call instead of clinic visit if no safety issue identified. ^D Phone contacts to assess tolerability and review diary/dosing instructions. ^E Pain assessment to be completed every 12 hours.

1.3. Study population:

Enrolled population: The group of subjects who sign informed consent.

Randomized safety population: The group of subjects who are randomized and receive at least 1 dose of the study drug and have at least 1 safety assessment.

Full analysis population: The group of subjects who are randomized, receive study drug, and have at least 1 valid efficacy measurement.

Per protocol population: The group of subjects who are included in the full analysis population but excluding those with major protocol deviations and those who do not receive the actual treatment they were randomized to receive.

Subjects and profiles/metrics excluded from the analysis set will be documented in the statistical analysis plan.

1.4. Efficacy Analysis

Listings, tables, and figures of efficacy variables will be based on the full analysis population.

1.4.1. Primary Efficacy Analyses

The baseline, post-baseline and change from baseline for bladder pain/discomfort scores over last 12 hours (morning and night) will be summarized by treatment group using descriptive statistics and presented graphically. Changes from baseline to endpoint in mean bladder pain/discomfort scores will be analyzed by mixed model with treatment, period and sequence as fixed effects, subject within the sequence as a random effect and baseline as a covariate. Comparison of the active treatment to placebo will be tested at the one-sided significance level 0.10 by means of the corresponding contrast. Plots of the least square mean change from baseline and 90% confidence intervals will be produced by treatment group.

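### Does section 1.4.1 have to name the diary days behind baseline and endpoint for the crossover contrast to be sound?

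*Combined protocol and SAP*

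**What the plan says.** Section 1.4.1 (Primary Efficacy Analyses) sets the primary analysis: "Changes from baseline to endpoint in mean bladder pain/discomfort scores will be analyzed by mixed model". The model terms that it then lists are "treatment, period and sequence as fixed effects, subject within the sequence as a random effect and baseline as a covariate". The test is one-sided at 0.10. The section does not tie baseline or endpoint to particular diary days.

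The Synopsis (1.1) describes a two-week single-blind placebo run-in, then "Double-blind Treatment Period (8 weeks), Single-blind Placebo Washout Period (1 week), and Follow-up Period". The schema shows the eight weeks as one block in which a subject takes V117957 or placebo, with no switch day and no washout inside it. Treatment durations are six weeks of V117957 and five of placebo.

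The Schedule of Assessments (1.2) has pain rated morning and evening throughout. For the void diary it names recording days: "During the week prior to each clinic visit (V3, V4, V5, V6, and V7), subject will record micturition time, type, and urgency". Its notes mark Visit 2, Day -1, as the end of the run-in and the start of double-blind treatment.

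On planning, the Synopsis says "A sample size of 38 (completers) will have 81% power to detect a treatment difference of bladder pain/discomfort mean scores of 0.5". That figure rests on a paired t-test, one-sided at 10%. Section 1.3 points to a further document for one matter: "Subjects and profiles/metrics excluded from the analysis set will be documented in the statistical analysis plan".

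**The concern.** Change from baseline in a crossover can mean two things: change from one run-in value that serves every period, or change from a value taken afresh before each period. The first is the same number in every period for a given subject. The second, where no washout separates the treatments, is measured on drug before a placebo period and on placebo before a drug period. The baseline then carries part of the treatment effect, and both subtracting it and adjusting for it can distort the contrast even with no carryover.

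The endpoint mean is open in a similar way. If every day of a short placebo period is scored, days just after a switch may still carry drug effect. If only late days are scored, the mean is noisier. If the choice were made after seeing unblinded results, the 10% error rate would not hold. At stake are the size of the one primary estimate and, to a lesser degree, its power and error rate.

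**Working it through.** **1. The plan's own figure.** Inputs from the Synopsis: n = 38, difference 0.5, SD of differences 1.4, one-sided 0.10. Noncentrality = 0.5/1.4 × √38 = 2.20 on 37 degrees of freedom. Power is 81.5% (82.1% by normal approximation), so the stated 81% reproduces.

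**2. Week count.** Treatments: 6 + 5 = 11 weeks. Run-in, double-blind block and final washout: 2 + 8 + 1 = 11 weeks. If the run-in and washout count as placebo, the block holds 5 − 2 − 1 = 2 placebo weeks. The plan does not state this split.

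**3. Baseline, two periods, no carryover.** Let τ be the true reduction in pain on drug and γ the slope of the raw score on baseline. Modelling the change score with baseline as covariate is the same as modelling the raw score with covariate, with the slope shifted by 1.

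- Run-in baseline: period-2 minus period-1 baseline is 0 for every subject. Baseline drops out and the contrast is τ.
- Re-taken baseline: the expected baseline difference is 0 for placebo-then-drug and −τ for drug-then-placebo. The adjusted period differences are −τ and τ + γτ. Half their difference is τ(1 + γ/2).

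For τ = 0.50 this gives 0.50 at γ = 0, 0.625 at γ = 0.5 and 0.75 at γ = 1. At τ = 0 it gives 0, so the bias scales the effect and does not create one.

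**4. Simulation of the 1.4.1 model (REML).** True difference 0.50, no carryover, SD of differences 1.4. Assumed: between-subject SD 1.0 to 2.0 and the layouts shown (P placebo, D drug). PD/DP: n = 38, 3,000 runs per case, plus n = 40 for the upper end of the re-taken range. Four-block layouts: n = 40, 1,500 runs, between-subject SD 1.0 and 2.0.

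| Layout | Run-in baseline: estimate | Re-taken baseline: estimate | Power, run-in to re-taken |
|---|---|---|---|
| PD/DP, two periods | 0.49–0.51 | 0.62–0.72 | 80–83% to 80–83% |
| PDDD/DDDP, four 2-week blocks | 0.498, 0.510 | 0.505, 0.488 | 70.8% to 69.6%; 73.3% to 58.6% |
| Four placebo placements, four 2-week blocks | 0.512, 0.500 | 0.519, 0.568 | 85.8% to 82.7%; 83.3% to 79.8% |

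In PD/DP the re-taken estimate is 23% to 43% too large (0.615/0.50 to 0.715/0.50). Its one-sided rejection rate under the null was 10% to 14% across runs, against 9% to 11% for the run-in baseline, so only the upper end is clearly inflated.

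**5. Carryover, run-in baseline.** Let c be the share of the effect that persists, averaged over the scored placebo days, and w the share of subjects whose placebo follows drug. The contrast is 0.5 × (1 − cw). Assume full persistence for 3 of 14 days (c = 3/14) and w = 0.5: 0.5 × (1 − 0.107) = 0.446, power 74.6%. A rebound of the same size gives 0.554. The documents give no value for c or w.

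**6. Cost of avoiding it with a late window.** Variance of the difference = 1.96 + Var(window means) − Var(all-day means). Moving from 42 drug and 14 placebo days to 7 and 7, with assumed daily SD 1.0 and independent days: 1.96 + 2/7 − (1/42 + 1/14) = 2.150, SD 1.466, power 78.7%. With daily SD 1.5, power is 72.2% at day-to-day correlation 0.3 and 65.6% at 0.7. The late window therefore costs about 3 to 16 points, against about 7 points (81.5 − 74.6) for the assumed carryover. Neither choice is clearly better.

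**7. Choosing the window late.** Taking the better of whole-period and last-7-day results after unblinding would raise the error from 10% to 12–15%. Nothing in the documents suggests that this is intended.

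**The case for a change.** The case for a change is respectable. Section 1.4.1 appears in full, so redaction does not explain the silence there, and the only pointer to an SAP concerns exclusions from the analysis set. A baseline that is constant within subject does nothing for a complete subject's contrast, so listing it as a covariate could hint that period baselines were meant. Two analysts working literally from 1.4.1 could report effects that differ by 23% to 43%. The cure would be a few sentences, with no new data and, on a run-in baseline, no loss of power.

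What stands: the days are not stated in the available text, and the algebra for a re-taken baseline is right. What does not stand is the step from silence to a fault. Section 1.4.1 speaks of baseline in the singular, no re-baselining is scheduled, and Visit 2 closes the run-in just before randomized treatment. A constant baseline covariate is common and harmless, and it helps with subjects who contribute only one period. The large distortion needs the less natural reading together with an unstated two-period layout.

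The void-diary comparison is weak. Those days say when subjects record, not which days are analysed, and pain is recorded every day and needs no such rule. Switch days may well be withheld to protect the blind.

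**Conclusion.** No change follows. The gap is one of detail: which run-in days make up baseline, and which days of each period make up endpoint. A statistician finalizing the analysis would take the run-in mean as baseline and fix the endpoint days before unblinding; on that reading the contrast is unbiased without carryover (0.49 to 0.51 for a true 0.50 in every layout tried). The endpoint window is a trade-off between carryover and noise, and the documents hold no figure that would settle it, so a review could only hand back blanks for the sponsor to fill.

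This rests on three conditions. Baseline is the single run-in value. The window is set before unblinding. The planned 81% is read as the power of a paired comparison of one mean per treatment. Of the other layouts, PDDD/DDDP gave 71% to 73% with 40 subjects even with a run-in baseline; that reflects the layout and not the definition of baseline. If the sponsor did intend a baseline re-taken on treatment in a two-period layout, the 23% to 43% overstatement would become real and the conclusion would have to be revisited. The carryover and window-selection figures are illustrations and do not show an error in this plan.

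### Does leaving the sequences, the period levels and the endpoint window undefined in 1.4.1 make the primary crossover contrast open to time drift?

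*Combined protocol and SAP*

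**What the plan says.** The Synopsis (1.1) describes a "Phase 1b, multicenter, randomized, double-blind, placebo-controlled, crossover study". Its Brief Summary gives the phases as "Single-blind Placebo Run-in Period (2 weeks), Double-blind Treatment Period (8 weeks), Single-blind Placebo Washout Period (1 week" and its treatment-duration line gives "V117957 (6-weeks) and Placebo (5-weeks" weeks in brackets. The Schema fills the whole double-blind phase with one cell, "V117957 or Placebo".

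Section 1.4.1 takes as its outcome "Changes from baseline to endpoint in mean bladder pain/discomfort scores" and fits a "mixed model with treatment, period and sequence as fixed effects, subject within the sequence as a random effect and baseline as a covariate", tested one-sided at 0.10. The sample size in the Synopsis was found "using a paired t-test with a 10% one-sided significance level", with 38 completers, a difference of 0.5 and an SD of differences of 1.4.

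No section supplied lists the treatment sequences, says how many levels *period* has, or says which diary days form the endpoint mean. Elsewhere the word names a study phase: footnote B of Table 2 says that Visit 2 "is end of Single-blind Run-in Period and start of the Double-blind Treatment Period".

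**The concern.** In a two-period crossover with equal periods, treatment, period and sequence need little explanation: both sequences are observed at the same two calendar times, and the period term absorbs any trend common to all subjects. Here exposure is 6 weeks against 2. If period simply means first or second treatment, its two levels fall at different calendar times in the two sequences, and the term can no longer remove a common trend from an end-of-treatment comparison.

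Symptom scores may drift after enrolment, through regression to the mean or placebo response. A drift of a few tenths of a point matters beside a planned difference of 0.5. There is also a freedom-to-choose worry: if several codings fit the text and give different answers, the choice could in principle be made with the result in view.

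**Working it through.** **Inputs from the documents.** Run-in placebo 2 weeks, double-blind 8 weeks, washout placebo 1 week; V117957 6 weeks and placebo 5 weeks; 38 completers, difference 0.5, SD of differences 1.4, one-sided alpha 0.10; clinic visits on Days 14, 28, 42 and 56.

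**Assumptions, since the documents give no figure.** Two equal sequences unless stated, equal correlation between 2-week blocks, and the drift, onset and carry-over shapes below.

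**1. The plan's own figure.** SE = 1.4/√38 = 0.227. The paired t-test with 37 df and noncentrality 0.5/0.227 = 2.20 has power 81%. The stated 81% reproduces.

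**2. Exposure.** 2 + 8 + 1 = 11 = 6 + 5. Double-blind placebo = 5 − 2 − 1 = 2 weeks, leaving 6 weeks of V117957. This is derived rather than stated, but it is the only split that fits if the durations apply to each subject.

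**3. Readings that fit the wording.** Let f be a pain trend common to all subjects, with f2, f4, f6 and f8 its values at the ends of the four 2-week blocks. Bias is V117957 minus placebo, so a negative value favours the drug.

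- *A: one switch, end-of-treatment value, two-level period.* Drug first gives f6 − f8; placebo first gives f8 − f2. The average is (f6 − f2)/2. SE 0.227.
- *B: one switch, all four block records, two-level period.* Bias = (f4 + f6 − f2 − f8)/3. Residual variance per record = 1.4²/2 = 0.98, so SE = √(0.98 × (1 + 1/3)/38) = 0.185.
- *C: one switch, four calendar periods.* Weights are ±0.5 on blocks 1 and 4 and zero on blocks 2 and 3. Bias is 0 for any common trend. SE = √(0.98/(38 × 0.5)) = 0.227.
- *D: placebo in block 1, 2, 3 or 4 over four sequences, four calendar periods.* Bias is 0. SE = √(0.98/(38 × 0.75)) = 0.185.

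**4. Type I error (nominal 10%), from the noncentral t.**

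| Assumed drift | A | B | C, D |
|---|---|---|---|
| None | 10% | 10% | 10% |
| Linear, fall of 0.2 from week 2 to 6 (A: bias −0.10) | 20% | 10% | 10% |
| Linear, fall of 0.4 (A: bias −0.20) | 34% | 10% | 10% |
| Linear, rise of 0.2 (A: bias +0.10) | 4% | 10% | 10% |
| 1-point exponential decline, 2-week half-life, from run-in (A −0.094, B −0.031) | 19% | 13% | 10% |
| Same, from randomisation (A −0.188, B −0.062) | 32% | 17% | 10% |

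**5. Power for a difference of 0.5.** With gradual onset, C keeps the average of the 2-week and 6-week shares of the effect: (0.571 + 1)/2 = 0.79 for a 2-week half-life, (0.333 + 1)/2 = 0.67 for linear onset over 6 weeks.

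| Onset | A | B | C | D |
|---|---|---|---|---|
| Immediate | 81% | 92% | 81% | 92% |
| Gradual, 2-week half-life | 81% | 81% | 67% | 76% |
| Gradual, linear over 6 weeks | 81% | 70% | 57% | 58% |

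For D, onset is taken to restart after the placebo block. If a share c of the effect carries over into placebo taken after drug, A and C keep 1 − c/2 of it: 88% or 75% for c of 25% or 50%, with power 73% or 64%.

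No reading is best on both counts. A keeps the full week-6 effect and is open to drift; C and D are closed to drift and pay for it when onset is slow.

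**The case for a change.** The strongest case for a change is that the gap is real and the choice matters. Section 1.4.1 carries no visible redaction, and the only matter the text expressly leaves to the statistical analysis plan (1.3) is exclusions from the analysis set. Reading A is not far-fetched: a paired t-test implies one value per treatment per subject, and endpoint is in the singular. Definitions cost only text, because the twice-daily diary already supplies the data.

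The unequal split, the absence of definitions from the supplied text and the arithmetic all stand. Three things do not follow.

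- *That the plan lacks the definitions.* Only section 1 is supplied, and parts of it are gone without a mark: numbering runs from 1.4.1 to 1.4.3, and footnote H of Table 1 has no text. Sequences may also be kept out of a synopsis to protect the blind.
- *That A is the intended reading.* Visits every 2 weeks, with drug dispensed along that schedule and a 2-week placebo share equal to one interval, suit calendar periods at least as well. The use of the same word for a study phase is a label, and does not contradict its use as a model factor.
- *That the terms would stay open until unblinding.* Nothing in the documents suggests this.

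**Conclusion.** The concern does not call for a change. The model named in 1.4.1 is a standard crossover model and is compatible with layouts in which common drift cancels exactly (C and D). The 20% and 34% error rates need reading A together with assumed falls of 0.2 and 0.4 points, so they show what could happen under one interpretation; they do not show a fault in the rule as written.

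The only substantive alternative, calendar periods as the primary coding, is a trade-off. In a one-switch layout it protects the 10% level but lowers power from 81% to 67% or 57% under the two gradual-onset assumptions, rests half the contrast on drug data from the first 2 weeks, and leaves the middle two blocks unused. Preferring it without knowing the sequences or the speed of onset would be a matter of taste in a Phase 1b study.

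What remains is a gap in description. The randomisation schedule fixes the sequences, and a statistician programming the model must set the period levels and the diary window, ordinarily before unblinding, in the analysis plan or the table specifications. If a fuller analysis plan already does so, nothing is missing beyond a cross-reference. This conclusion rests on the durations applying to each subject and on the supplied text being only part of the plan.
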